Essex Coronavirus Action Support (ECAS) involves collaboration between Essex County Council (ECC) and The Essex Public Health Team as well as local Facebook groups. It focuses on the provision of three services: *preventing* the spread of infection, *informing* Essex residents of guidance and *assisting* residents who may be vulnerable. The ECAS Facebook page which was created on 14th March 2020 ('Essex Coronavirus Action', 2020) is now followed by 55,339 people (at the time of writing) and is used to distribute information to the community. The related private group created on 15th March 2020 has approximately 37,900 members ('Essex Coronavirus Action Support', 2020) and is described as a space for residents of Essex, promoting connection and discussion about issues related to the COVID-19 pandemic.

When membership of the ECAS group is requested, admins ask for a postal code to verify people are Essex residents, members are not actively recruited. Whilst approximately 80% of the demographic is female, men have been reported to be over-represented in discussion ('Mobilizing Essex residents', 2020). There are 18 community admins who oversee the private group, three have a prominent role with ECC paying for their work. Issues around misinformation are dealt with on a case-by-case basis and in rare instances members are banned/ muted if promoting argument.

Growth, recruitment and management have been described as evolving intuitively and some research has been conducted to capture decisions explicitly in terms of team roles, structure and the organisational environment ('Essex County Council', 2021). The co-produced logic model illustrating resources, activities and outcomes as well as their connection (shown in Figure 1) guides the current evaluation of the ECAS intervention.

The proposed evaluation will combine quantitative (Work Package 1, see *Methods* below) and qualitative (Work Package 2) methods to understand the extent to which ECAS achieved its aims to facilitate 'prevent, perform and assist' and also the wider impact it has had on public health system approaches.

Rationale

Promoting behavioural change

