Effects of ECAS and underlying processes: For those that have joined ECAS, we will test how engagement with the ECAS Facebook page and group relates to (i) a sense of social connection and (ii) how both engagement and the sense of social connection relate to the interim outcomes of increased health literacy, covid protective behaviour and community champion activity (see Figure 2). A further analysis will compare levels of each of these factors amongst those who did engage with the intervention versus a comparator group who did not and across socio-demographic groups if the data allows (i.e., using moderation analyses). Amongst both samples, we will also measure current levels of mental health and test relationships between these and each factor. These analyses will provide a quantitative evaluation of the extent to which the intervention met its aim to ‘inform’, ‘prevent’ and ‘assist’. Additionally, for those who engage in it, it will also identify which interim outcomes were most impacted and the extent to which this effect was mediated by social connection.

[figure not shown]

Figure 2: Primary conceptual model to be tested.

Given the nature of the study, much of these data will be retrospective (i.e., people’s recollection of their behaviours). In these instances, we will ask participants to recall how they felt during what our preparatory work with stakeholders (stakeholder workshops and also a PPIE workshop), identified as a *critical phase* of the intervention’s deployment. The critical phase selected for the quantitative analysis of new data is the the first two weeks following the lifting of the first lockdown.

Table 1 (see below) indicates broad operationalisations of each of the factors, the source of data (and whether it is current or retrospective) and possible measurement instruments.

Table 1: Indicative primary outcome measures¹

Factor	Operationalisation(s)	Source of data	Indicative instrument
Interaction with ECAS	Did / did not engage with site Intensity of engagement (users only)	Facebook data or self-report	Study generated scale/metrics
Social connection	Sense of social connection with others Collective responsibility	Self-report (current) Self-report (critical phase)	Validated scale (Lee, Draper & Lee, 2001)
Health literacy	Level of perceived digital health literacy	Self-report (current)	Use of two subscales: information searching and evaluating reliability from validated scale (Van der Vaart & Drossaert, 2017)

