COVID protective behaviours	Engage in behaviours which are likely to reduce infection risk to self and others	Self-report (critical phase)	Items from Freeman et al. (2020)
Community champion activity	Helped others practically in real world Signposted to online reliable information Corrected misinformation online	Self-report (critical phase)	Study generated scale
Mental health	Level of anxiety Satisfaction with life COVID specific anxiety syndrome	Self-report (critical phase)	GAD-7 (7 items) PHQ-9 (9 items) SWLS (~5 items) Nikčević & Spada (2020)
	Level of anxiety	Self-report (current state)	GAD-7 (7 items)

¹ Use of tools is subject to securing permissions, where required, from authors.

The relationships highlighted in Figure 2 will be analysed using the Hayes PROCESS macro tool (Hayes, 2018), focusing on one effect and mediation per model (see power analysis below for a rationale).

This aspect of the research will also take additional *secondary outcome measures* from those who engaged with ECAS including *sense of ownership of the site* (self, community, local authority), *understandings of information provenance*, *confidence in information*, *frequency of referrals made to the site* and *reliance upon site*. This will allow exploratory testing of how these factors relate to the efficacy of the intervention. These will need to be short measures (i.e., single item scales) given the length of the primary outcome measures and subsequent possible impact upon participant attrition.

Analysis of existing data

Social network analysis: We will explore the feasibility of using social network analysis (SNA) to see the extent to which influence (categorised as interactions) in the network is central (via admins out to members) or distributed (member to members, including core member and peripheral members) over a given time period (see *Sampling*, below). Data will be analysed using the SNA package on R.

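### In the members-only model, signposting or correcting done inside ECAS can count both as engagement and as community champion activity, which can inflate their association

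*Protocol*

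**What the plan says.** All of this is in the protocol, under Study design, methods and analyses, Work Package 1, unless stated.

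- **Exposure.** Table 1 operationalises interaction with ECAS as "Did / did not engage with site Intensity of engagement (users only"), with source and instrument given as "Facebook data or self-report Study generated scale/metrics". No items are listed.
- **Outcome.** Table 1 operationalises community champion activity as "Helped others practically in real world Signposted to online reliable information Corrected misinformation online", by self-report for the critical phase on a study-generated scale.
- **Members-only analysis.** The plan tests "how both engagement and the sense of social connection relate to the interim outcomes of increased health literacy, covid protective behaviour and community champion activity". For those who engaged, "it will also identify which interim outcomes were most impacted and the extent to which this effect was mediated by social connection".
- **Between-sample analysis.** Separately, the investigators plan to "compare levels of each of these factors amongst those who did engage with the intervention versus a comparator group who did not".
- **What happens inside ECAS.** Under The intervention of interest, the private group is described as "promoting connection and discussion about issues related to the COVID-19 pandemic", and misinformation arising there is said to be handled individually. Work Package 2, qualitative component 1, names sharing information as one of the roles a member may take.

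Nothing limits the signposting and correcting components to acts outside the ECAS page and group, and nothing removes such acts from the engagement measure.

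**The concern.** On the protocol's own description, posting a reliable source or correcting a false claim in the group is a way of taking part in ECAS. It also scores on the champion scale. If the intensity metric counts posts or comments, exposure and outcome share content, and members who post more will score higher on both whether or not ECAS changed how much they help or inform others.

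Two conclusions are at stake. The engagement-champion association could be read as ECAS building mutual aid when it shows only that active members are active. And the plan compares outcomes to see which was most affected: COVID protective behaviours are not made up of Facebook posts, so champion activity has an advantage in that ranking that is purely a matter of measurement.

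**Working it through.** **1. The plan's own figure.** Under Size of sample the protocol gives power 0.81 for a single mediation effect with n = 225 and r = .30 between all variables. No alpha is stated; two-sided .05 is assumed here. With a = .30 and b = (.30 − .09)/(1 − .09) = .231, the Sobel statistic is 2.82 and power is Φ(2.82 − 1.96) = 0.81. The figure reproduces and is not in dispute. It supplies the benchmark r = .30.

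**2. Closed-form size of the overlap.** Every input here is an assumption, as the protocol gives none of them. Three equally weighted standardised components; inter-item r = .30; no ECAS effect on acts outside ECAS; s = share of the variance of each of the signposting and correcting items that comes from acts inside ECAS; c = correlation of those inside acts with engagement (.4 to .6).

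- Item-engagement correlation: ρ = c√s.
- Composite correlation: r = 2ρ/√(3 + 6 × .30) = 2ρ/2.191.
- Chance that a simple correlation test is significant at n = 225: Φ(√222 × atanh r − 1.96).

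| s | ρ (c = .4; .6) | r (c = .4; .6) | Declared significant |
|---|---|---|---|
| .10 | .126; .190 | .12; .17 | 41%; 74% |
| .25 | .200; .300 | .18; .27 | 79%; 99% |
| .50 | .283; .424 | .26; .39 | 98%; 100% |

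This version still allows ECAS to have generated extra acts inside the group, so it is not a strict null.

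**3. A strict null, by simulation.** Each member's total of online champion acts is fixed, so ECAS changes nothing. The share done inside ECAS is independent of that total. Engagement is the inside acts plus unrelated ECAS activity, and real-world help is independent of everything. Entries are the correlation of engagement with the full three-part score, then with the score counting only outside-ECAS acts.

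| Acts done inside ECAS | Champion acts 10% of engagement | 25% | 50% |
|---|---|---|---|
| 0% | .00; .00 | .00; .00 | .00; .00 |
| 10% | .088; .028 | .161; .057 | .227; .075 |
| 25% | .125; .038 | .228; .070 | .348; .110 |
| 50% | .152; .039 | .297; .081 | .469; .125 |

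Across the rows with any inside acts, the full score is significant at n = 225 in about 26% to nearly 100% of studies. The outside-only score leaves a residual of .03 to .13. Real-world help gives zero, by construction.

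**4. The indirect effect.** With X engagement, M social connection and Y champion activity, b = (r_MY − r_XM × r_XY)/(1 − r_XM²). If connection depends only on overall engagement, r_MY = r_XM × r_XY. For example, with r_XM = .30 and a spurious r_XY of .39, r_MY = .30 × .39 = .117 and b = (.117 − .117)/.91 = 0. The overlap then sits wholly in the direct path, and hence in the total. b rises above zero only if r_MY exceeds r_XM × r_XY, that is, if connection tracks signposting and correcting posts over and above general engagement.

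**5. The between-sample difference.** Let both samples have the same total T, with members doing a fraction f inside ECAS. Totals are T and T, so the difference is zero. Counting only outside acts gives members (1 − f)T against T for comparators: 10% to 50% lower for f of 10% to 50%.

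**The case against.** The strongest reply is that the overlap depends on an exposure measure the protocol has not yet fixed. Intensity might be built from visits, reading or reactions, and Work Package 2 recognises members who mostly read. Table 1 is labelled indicative, and item wording belongs in the questionnaire. This stands in part: the artefact is largest if posts and comments are counted and smaller if they are not. It does not dispose of the point, because analysis cannot later separate acts whose place was never recorded.

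Second, signposting to online information need not be an online act; telling a neighbour about a website would score. That is right and reduces the overlap on that component. Correcting misinformation online has no such reading.

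Third, members informing one another inside the group may be a legitimate goal of a digital community intervention. It may be, but an act counted as participation cannot also serve as evidence that participation changed behaviour. Reporting it separately keeps it in view.

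Two stronger readings are tempting and are not supported. A reader might infer that mediation by social connection is inflated as well; by step 4 this needs an added assumption about connection that the protocol does not supply. A reader might also infer that the ECAS-versus-comparator difference is inflated. Comparators are Facebook users who can do the same acts elsewhere; acts merely moved into ECAS leave totals equal, and a higher total caused by ECAS would be a real effect.

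**Conclusion.** The concern holds for the members-only analysis. As Table 1 stands, the same act can enter both engagement intensity and champion activity, so their direct or total association, and champion activity's place in the ranking of outcomes, can be inflated with no effect of ECAS.

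The size cannot be known from the protocol. Under the assumed inputs the spurious correlation is roughly .1 to .4 (.12 to .39 in closed form; .09 to .47 in the strict-null simulation), so it can reach the r = .30 the study is powered for. It disappears if no champion acts take place inside ECAS, or if the intensity metric leaves such posts out and the rest of engagement is unrelated to champion activity. The detection rates describe a simple correlation test, not the planned mediation test. The stated power of 0.81 is unaffected.

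**What to change.** - **Questionnaire.** In the study-generated champion scale, ask about signposting and correcting separately for acts inside the ECAS page or group and acts elsewhere.
- **Members-only engagement and mediation models.** Use real-world help plus outside-ECAS acts as the champion score, or else leave signposting and correcting posts out of the intensity metric. Report real-world help alone as the check free of overlap, since the outside-only score can keep a small residual association.
- **Between-sample comparison.** Keep total activity, inside plus outside, and show the outside-only score alongside it. Dropping in-ECAS acts altogether would bias the contrast against ECAS if acts were displaced into the group.

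The cost is one or two extra short items on a scale the study is writing itself, and probably a smaller members-only estimate. No added sample or change to a licensed instrument is needed. It has to be settled before the survey is fielded; the Milestones table has data collection complete by November 2021.

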Sentiment analysis: Sentiment analysis, through use of Linguistic Inquiry and Word Count (LIWC) software, will computationally assess affective change for individuals using the ECAS Facebook group. The corpus will be consistent with that selected for psychological discourse analysis within Work Package 2 (see below), for consistency, to enable triangulation and heighten human monitoring of content. Our evaluation will test the extent to which negative affect in member discussion around protective health action topics decreased over time between the critical periods, and also the extent to which positive affect in response to ECAS dissemination of public health messages increases.

Health equity: To evaluate how widely and amongst how diverse a population the intervention was accessed we will compare the demographic of people using ECAS against the demographic profile of Essex. This analysis will include data from the core provision (Facebook) but also other platforms where ECAS presented information (i.e., Instagram, Twitter).

Work Package 2: Qualitative work package

The qualitative strand of the project will examine which factors were important in contributing to the outcomes of:

- Achieving improved health literacy;
- Encouraging protective health actions;
- Enhancing community connectedness and mutual aid.

It will also explore how the digital community development approach sought to achieve whole system change for the public health function.

The overall approach is *digital ethnography*, also known as online or cyber ethnography, which seeks to study online communities and their cultures (Caliandro, 2014). It adapts the traditional methods of participant observation, interviews, documentary analysis and surveys

to studying online communities. Digital ethnography will be used to analyse online interactions between people connected through technology.

The qualitative work stream will have two components:

Qualitative component 1: Participant observation of Facebook interactions analysed using discourse analysis:

Facebook interactions in the form of posts and comments will be analysed using psychological discourse analysis (Goodman, 2017) to analyse how communication is used to mobilise social action, e.g., framing authority differently to engage members to collective action. The analysis will focus on what has been achieved through conversations rather than what the members are thinking.

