Previous research about building online communities has identified discursive strategies such as affective responses (use of humour, expressing emotions, self-disclosure), interactive responses (continuing a thread, quoting others, asking questions, expressing agreement) and cohesive responses (addressing the group using 'we' and 'us', using names; Rourke, Anderson, Garrison & Archer, 1999).

The analysis will focus upon:

- How communication seeks to mobilise social action and promote members to engage in protective health actions;
- Examine the extent to which influence (categorised as interactions) in the network is central (via admins out to members) or distributed (member to members, including core member and peripheral members).

The Facebook discussions during the chosen time periods will be anonymised, exported as data files and imported into NVivo qualitative data analysis software. There will be three researchers who will be responsible for data analysis and this will commence with separate analysis of initial data and meetings to compare analysis and develop a shared coding framework.

The sub-questions that will be the focus are:

1. What discursive devices were used to:
 - a. Build and maintain an online community?
 - b. Encourage members to engage in protective health actions?
 - c. Contribute to community connectedness and mutual aid?

Based upon PPIE feedback, the analysis will include what role members adopt, e.g., as info gatherer, info sharer, for support and discussion. The analysis will be informed by a typology of roles identified in the literature, e.g., 1) sporadics; 2) lurkers; 3) socialisers; 4) debaters; 5) actives (Brandtzaeg & Heim, 2011).

2. How do these forms of discursive practice contribute towards achieving whole system change for the public health function?

Qualitative component 2: semi-structured interviews with:

- a. Key Essex County Council staff who designed the intervention
- b. Essex Public Health Team
- c. Facebook admins

Interviews will focus on understanding how the approach seeks to achieve its goals through social media and how these online communities can be used to mobilise social action and mutual aid. Interviews will be transcribed and analysed using framework analysis (Gale, Heath, Cameron, Rashid & Redwood, 2013).

Work Package 3: Economic evaluation

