Work Package 2: Sampling techniques for each aspect are detailed in Table 2.

Table 2: Recruitment methods for Work Package 2

Research method	Sample and sampling technique
Discourse analysis of online Facebook conversations	
Facebook posts, comments and discussions will be analysed in samples of 1-2 weeks at key points:
 
• The initial lockdown and set up phase (March-April 2020)• Interim period between the first and second lockdowns (July/August 2020)• The second lockdown (Oct-Nov 2020)• Interim period between the second and third lockdowns (July/August 2020)• The third lockdown (Jan 2021) 
This will enable the analysis of each lockdown as well as comparison with lower activity periods between these active periods

Qualitative semi-structured interviews	
A total population sampling strategy will be used to purposively sample all staff within Essex Public Health and the Facebook admin team:
 
Key Essex County Council staff who designed the intervention (n = 5-6)
 
Facebook admins (n = 6-8)
 
Wider staff within the Essex Public Health team (n = 6-8)
 
Total sample = 17-22 participants

Sampling technique

Work Package 1: The study will draw upon a convenience sample of individuals recruited from the ECAS platform, and the comparative sample from Facebook in line with the inclusion and exclusion criteria above. Our health equity analysis will help us to evaluate the extent to which the chief samplers are representative of the ECAS population and the wider population of Essex. Should the sample be non-representative, we will explore the need to weight responses accordingly.

Social network analysis: Purposive sampling will be undertaken to capture representative patterns of activity - please see *Sampling* (above).

Work Package 2: See Table 2 for sampling techniques.

Recruitment

Work Package 1: Where new data are collected, we will recruit directly for the ECAS group via a series of posts promoting the study. For the comparator sample, a range of community Facebook groups will be contacted (with permissions to post sought from moderators where the group's usage terms require this), supported by paid posts promoting the study to the target population. We will incentivise both groups via use of vouchers.

For the *social network analysis*: please see *Sampling* (above).

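### The test for falling negative affect is confounded with lockdown status: the sampled periods alternate lockdown and interim, and the periods to be compared are not defined

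*Protocol*

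**What the plan says.** In the Protocol, Analysis of existing data, Sentiment analysis, LIWC software "will computationally assess affective change for individuals using the ECAS Facebook group". The evaluation is to test the extent to which "negative affect in member discussion around protective health action topics decreased over time between the critical periods", and a companion test asks whether positive affect in response to ECAS messages rises.

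The text to be analysed is fixed by reference: "The corpus will be consistent with that selected for psychological discourse analysis within Work Package 2". Table 2 lists that sample as five periods of one to two weeks each. The first two are "The initial lockdown and set up phase (March-April 2020") and "Interim period between the first and second lockdowns (July/August 2020"). They are followed by the second lockdown (Oct-Nov 2020), an interim between the second and third lockdowns, and the third lockdown (Jan 2021). The second interim carries the same July/August 2020 date as the first. Table 2 gives the purpose of this layout: "This will enable the analysis of each lockdown as well as comparison with lower activity periods between these active periods".

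On handling of the text, Qualitative component 1 says: "The Facebook discussions during the chosen time periods will be anonymised, exported as data files".

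**The concern.** The test is directional, runs over time and uses only text written inside ECAS. No outside text, reference series, adjustment for lockdown status or rule for comparing like periods is described. The comparator group under Sampling is a survey sample and supplies no Facebook text.

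Mood in a lockdown and mood between lockdowns may well differ for reasons that have nothing to do with ECAS. Because the five periods alternate, any comparison of neighbouring periods is also a comparison of lockdown with no lockdown. The choice of pair is open, because the term critical periods is not defined for this analysis. The survey uses one critical phase, the social network analysis uses two periods, and Table 2 lists five.

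At stake is whether a reported fall or rise in affect says anything about ECAS. A second question is whether change can be reported for individuals at all, given that no code linking a member's posts across periods is described.

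**Working it through.** The Protocol gives no sample size, effect size or power for the sentiment analysis, so there is no figure to reproduce. The check asks what the test would show if ECAS did nothing.

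**Inputs**
- Order and status of the periods (Table 2): lockdown 1 (L1), interim 1 (I1), lockdown 2 (L2), interim 2 (I2), lockdown 3 (L3).
- Text source (Sentiment analysis): ECAS group only.
- Assumption: no ECAS effect, and mean negative affect higher by d in lockdown than in an interim. The documents give no value for d; results are in units of d.

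**Step 1, adjacent changes.** Expected levels are d, 0, d, 0, d. The four adjacent changes are -d, +d, -d, +d.

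**Step 2, the whole series.** First to last: d - d = 0. Least-squares slope over equally spaced times 1 to 5 (mean 3): (-2d + 0 + 0 + 0 + 2d) / (4 + 1 + 0 + 1 + 4) = 0/10 = 0.

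**Step 3, every pair in Table 2 order.** Five periods give ten pairs.
- Lockdown to a later interim (L1-I1, L1-I2, L2-I2): three apparent falls of d.
- Interim to a later lockdown (I1-L2, I1-L3, I2-L3): three apparent rises of d.
- Like with like (L1-L2, L1-L3, L2-L3, I1-I2): four changes of 0.

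**Step 4, calendar dates.** Number the months from January 2020 = 1 and place each period at its midpoint (assumption).
- Dates as printed: 3.5, 7.5, 10.5, 7.5, 13; mean 8.4. Slope = d(-4.9 + 2.1 + 4.6) / (24.01 + 0.81 + 4.41 + 0.81 + 21.16) = 1.8d/51.2 = +0.035d per month.
- Second interim placed at December 2020 (assumption): 3.5, 7.5, 10.5, 12, 13; mean 9.3. Slope = d(-5.8 + 1.2 + 3.7) / (33.64 + 3.24 + 1.44 + 7.29 + 13.69) = -0.9d/59.3 = -0.015d per month.

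Both slopes are small, but the sign turns on the one date in Table 2 that cannot stand as printed.

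**Step 5, what like-with-like does not remove.** Add, for illustration, a decline unrelated to ECAS of 0.05d per month. The two slopes become 0.035d - 0.05d = -0.015d and -0.015d - 0.05d = -0.065d per month. Lockdown 1 against lockdown 3 shows (13 - 3.5) x (-0.05d) = -0.475d. Matching periods removes the swing of d but leaves any general trend.

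**Individuals.** Sentiment analysis promises change for individuals. Qualitative component 1 says the discussions will be anonymised and exported, and mentions no code that follows a poster from one period to the next. Without such a code, a change in who posts cannot be separated from a change within a person.

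**The case against.** - **Attribution.** A reader might infer that the Protocol will report a fall as an ECAS effect. It does not say so; it says only that the extent of the decrease will be tested. The inference comes from the setting: the analysis sits in the work package introduced as testing how engagement with ECAS affects outcomes, only favourable directions are named, and nothing marks the result as descriptive.
- **Size.** A reader might also infer that the pandemic alone produces the fall. Steps 1 to 3 do not support that. The series begins and ends in lockdown, so alternation by itself gives no net change and no trend over equally spaced periods. It gives a fall in some pairs and an equal rise in others.
- **Table 2.** Its contrast between period types concerns activity, not mood, and it already provides for analysis of each lockdown. That is correct, and it means matched comparisons are available from the planned sample. The Protocol does not require them.
- **Member codes.** It would be wrong to say that no code is kept. Data protection and patient confidentiality allows pseudo-anonymous data and key files, and the planned analysis of members' roles would be hard without some linking of posts. What stands is that no link across periods is described.
- **Level of detail and weight.** An analysis plan that is not at hand may fix the contrast, and this is a supporting analysis beside a survey with a comparator. Both are fair. But the corpus, the direction of the test and the anonymisation are set in the Protocol, and a link lost at anonymisation may not be recoverable later.

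**Conclusion.** The point holds as one of confounding and an undefined contrast. Each adjacent comparison changes lockdown status, so under a lockdown effect d and no ECAS effect the answer is -d or +d according to the pair chosen, and 0 from first to last. The course of the pandemic could produce a fall or hide one, and the result cannot be attributed to ECAS. This rests on the assumption that lockdown status shifts negative affect at all; the documents give no size for that shift or for any background trend.

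The documents do not support the stronger claims that a fall is bound to appear, that the Protocol commits to crediting ECAS with it, or that member codes are discarded. The duplicated interim date is a plain inconsistency: a period said to lie between the second and third lockdowns is dated before the second.

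**What to change.** 1. In Table 2, reconcile the dates of the two interim periods. Interim cannot be compared with interim until this is done.
2. In Sentiment analysis, define the critical periods for this analysis and make the contrasts like with like: lockdown 1 v 2 v 3, and interim v interim. Apply the same contrasts to the positive-affect test.
3. State that the results are descriptive and not evidence of an ECAS effect, since matching reduces but does not remove the pandemic trend.
4. Either drop the words promising change for individuals and report group-level change, or keep a pseudonymous poster code across periods and report within-member change. The second option needs agreement from the PPIE panel and the ethics panel, because PPIE acceptance of use without consent rested on anonymised data (Ethical oversight, Work Package 2). It should be settled before the Facebook text is harvested, which the Milestones put at September 2021.
5. A comparison with other threads in the same group and weeks may be added as exploratory only. Those threads are also exposed to ECAS, and nothing shows that pandemic mood moves equally in both kinds of thread, so the subtraction cannot be relied on to isolate an ECAS effect.

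The cost is mainly Protocol wording and a corrected date, plus the panel consultations if a code is kept. The downside is fewer contrasts and a weaker claim.
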